#### **Functional Living Index Emesis (FLIE)**

This is an 18-item Likert-type scale measuring the impact of chemotherapy-induced nausea and vomiting on patients' daily function. It is a commonly used scale in antiemetic trials.

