#### Appendix 4 FLIE questionnaire (English version)

### Functional Living Index - Emesis PATIENT INSTRUCTIONS

In the following questionnaire you are asked to rate how much nausea and vomiting have affected your quality of life. The first set of 9 questions refers to nausea and the second set of 9 questions refers to vomiting. The questionnaire should take approximately 10 minutes or less to complete. Please read the instructions before you begin. Think carefully about each question because your answers may help to develop treatments that will improve the quality of life for future patients.

[figure not shown]
For each question, you will rate how much nausea (or vomiting) has affected an aspect of your quality of life during the past five days. Please focus on your experiences **over that time period**. We are interested in **your opinions**, not those of family members or friends. Your answers will remain confidential.

You must answer every question. Use a black ball point pen and press firmly so that your mark is clear.

[figure not shown]
If you are unsure of your answer or do not understand the question, read the question again carefully and make a vertical mark (|) on the line based upon your best understanding of the question. If you want to change your answer, please do the following: make a new vertical mark (|); draw an arrow to the correct mark; initial and date the correction.

Each question uses a visual analogue scale. Think about how you rate your feelings and place a vertical mark (|) on the line at a point corresponding to how much your nausea (or vomiting) has affected that aspect of your quality of life. **Please read the question carefully because in some questions, a "1" indicates no effect on your quality of life and in other questions a "1" indicates a great deal of an effect on your quality of life.** You may place your vertical mark (|) at any point along the line. Be sure that you make your vertical mark (|) so that it intersects the horizontal line. Do not circle a number. Use a single vertical mark (|) as shown below.

[figure not shown]

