7.9. Rules and Formulas for Derived Variables

The CINV score will be calculated and used to identify patients with high risk of CINV. The calculation of CINV score will be done using following rules:

Predictive factor	Before a cycle of chemotherapy
Baseline score	10
Impact of patient risk factors	
Patient < 60 age	+1
Expectation (anticipation) of nausea and/or vomiting	+1
Patient has a history of morning sickness during a previous pregnancy	+1
Patient is about to receive platinum or anthracycline chemotherapy	+2
Patient used non-prescribed antiemetics at home in the prior cycle	+3
Patient has nausea or vomiting in the prior cycle	+5
About to receive the 2 nd cycle	-5
About to receive ≥ 3 rd cycle	-6

Since only the year of birth is available, the age of the patients will be calculated as the difference between the date of the screening and the first of January of the recorded year of birth.

The FLIE total score will be calculated from the corresponding questionnaire. The total score is the result of summing the responses to the 18 questions as the sum of the nausea and vomiting domain scores [5]. At least 12 of the 18 FLIE items (i.e., $\geq 66\%$ overall item response rate) must be non-missing, and both the vomiting and nausea domains must be non-missing, to calculate a FLIE total score. The score for domains (Nausea, Vomiting) will be also presented. At least 5 of the 9 FLIE domain items (i.e., $> 50\%$ overall item response rate) must be non-missing to calculate a FLIE nausea / vomiting domain score. Because the scale anchors are in the opposite direction on items 3, 6, 11, 15, and 18, the sensitivity analysis will be performed to assess the impact of incorrect responses. To assess the impact of these errors, the invalid item(s) will be set to missing before calculating the domain and total scores.

- Invalid nausea response: Set item 3 and/or 6 to missing if the item(s) are $\pm 50\text{mm}$ or more from the mean of items 1, 2, 4, 5, 7, 8, and 9.
- Invalid vomiting response: Set item 11, 15, and/or 18 to missing if the item(s) are $\pm 50\text{mm}$ or more from the mean of items 10, 12, 13, 14, 16, and 17.

The MAT scale for overall phase will be created by pooling the data from acute and delayed phases.

8. Flow of Patients and Specifications for analysed Populations

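### SAP 7.9 sums FLIE items with no rescaling rule for incomplete forms, and leaves the recoding of five opposite-anchored items unwritten

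*SAP*

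**What the plan says.** SAP 7.9 gives one operation for the score: "The total score is the result of summing the responses to the 18 questions as the sum of the nausea and vomiting domain scores", followed by a citation of reference [5]. The questionnaire in Protocol Appendix 4 fixes the domains: "The first set of 9 questions refers to nausea and the second set of 9 questions refers to vomiting".

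SAP 7.9 then lets incomplete forms be scored. The total needs "At least 12 of the 18 FLIE items" with both domains available, and a domain needs "At least 5 of the 9 FLIE domain items". It does not say how a sum over fewer items is brought back to the full scale.

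On item direction, SAP 7.9 says: "Because the scale anchors are in the opposite direction on items 3, 6, 11, 15, and 18, the sensitivity analysis will be performed". The patient instructions agree: "in some questions, a '1' indicates no effect on your quality of life and in other questions a '1' indicates a great deal". In that sensitivity analysis, items 3 and 6 are compared with the mean of the other seven nausea items, and items 11, 15 and 18 with the mean of the other six vomiting items. An item 50 mm or more away is treated as missing, and the scores are then computed. No sentence in either document says that the five items are recoded, what the item range is, or whether a high score is good or bad.

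SAP 9.1.3 provides for multiple imputation and LOCF on efficacy endpoints and for incomplete dates, and excludes imputation of anything else.

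**The concern.** A plain sum is safe only when every item is present. Once partial forms are admitted, the score depends on how many items were answered as well as on what was answered. The sensitivity analysis makes this worse because it creates missing items on forms that were complete, so its result mixes the correction of misread items with the loss of their contribution to the sum.

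The unwritten recoding is a second gap in the same derivation. SAP 9.1.5 calls for double programming of the secondary efficacy analyses. Two programmers could take the text at its word, or differ and settle the scoring after open-label data have been seen.

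FLIE is the only quality-of-life instrument among the secondary endpoints (SAP 6.2), and SAP 5.1 names it as the measure of the effect of CINV on daily activities and quality of life.

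**Working it through.** **Inputs.** From SAP 7.9 and Protocol Appendix 4: 18 items, 9 per domain; opposite anchors on 5 items (2 nausea, 3 vomiting); minimum counts of 12 of 18 and 5 of 9; a 50 mm limit. The item range is not stated, so 1-7 is assumed, with 0-100 mm as the alternative.

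**1. The plan's own figures.** 12/18 = 66.7% and 5/9 = 55.6%. Both agree with the percentages in SAP 7.9.

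**2. Partial forms.** Points lost = number of blanks × mean response. For uniform answers the proportional loss is blanks/18 (or blanks/9 in a domain), whatever the unit. At 7 per item:

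| Items answered | Plain sum | Rescaled | Shortfall |
|---|---|---|---|
| 18 | 126 | 126 | 0% |
| 17 | 17×7 = 119 | 126 | 5.6% |
| 15 | 15×7 = 105 | 126 | 16.7% |
| 13 | 13×7 = 91 | 126 | 27.8% |
| 12 | 12×7 = 84 | 126 | 33.3% |
| Domain, 5 of 9 | 5×7 = 35 | 63 | 44.4% |

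At 1 per item with 12 answered, the sum is 12 instead of 18, a loss of 6 points against 42 in the table. The loss in points therefore also depends on the patient's level.

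**3. Sensitivity analysis.** Deleting all five items leaves 9−2 = 7 nausea and 9−3 = 6 vomiting items, 13 in all. Both thresholds are still met, so the form is scored. Against a rescaled score from the same answers, the shortfall is 5/18 = 27.8% for the total, 2/9 = 22.2% for nausea and 3/9 = 33.3% for vomiting. The visible shift from the main score depends on the deleted values. Take a no-impact patient (7 on every item after recoding) who misread all five. The main sum is 13×7 + 5×1 = 96, and after deletion it is 13×7 = 91. Rescaling would give 126. The check should undo the misreading, but here it moves the score further from 126.

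**4. What the 50 mm check implies.** Without recoding, on a 0-100 mm line, a consistent and correct reader at x on the majority items has 100−x on the opposite ones. The gap |x−(100−x)| reaches 50 when x ≤ 25 or x ≥ 75, so that reader is flagged. A reader who overlooked the reversal has a gap of 0 and is not. The check does its stated job only after recoding.

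**5. Consequence if the sum were coded literally.** With 7 as no impact, the total runs from 13×1 + 5×7 = 48 (worst) to 13×7 + 5×1 = 96 (best), a range of 48. The correct range is 126−18 = 108, and 48/108 = 44%. The general share is (n−2k)/n: 8/18 = 44% for the total, 5/9 = 56% for nausea, 3/9 = 33% for vomiting. On 0-100 mm it is (1300−500)/1800 = 44%.

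The variance shrinks too. For unit-variance items with common correlation ρ and m = n−2k, the standardised effect relative to correct scoring is

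[m/√(n+ρ(m²−n))] / [n/√(n+ρ(n²−n))].

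With ρ from 0.3 to 0.9 (assumed) this is 0.83-0.99 for the total, 0.83-0.99 for nausea and 0.62-0.96 for vomiting. The direction of effect is kept.

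**The case against.** Three arguments deserve weight.

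First, a reader might infer that the SAP orders unreversed answers to be summed, that the 50 mm check works backwards, and that more than half of any treatment effect is lost. The documents do not support this. SAP 7.9 does not say that responses are used unreversed, its check makes sense only on recoded items, and it cites a scoring reference that is not available here and may cover both direction and rescaling. The 44% describes the score range on a literal reading, and the standardised loss is much smaller. This argument stands: the recoding is implied but not written.

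Second, blanks may be few. The form tells patients to answer everything, Protocol 3.6.3 has the investigator complete missing answers with the patient at Visits 2 and 3, and Protocol section 14 ties site payment to complete data. This limits the effect on the main score, where one blank costs 5.6%. It is weaker for cycle 3: the Visit 4 text mentions only checking, and the form is due on Day 6 although Visit 4 may fall on Day 5. It does nothing for the sensitivity analysis, which deletes items from complete forms.

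Third, SAP 7.9 is silent on rescaling, and silence does not mean that blanks count as zero. But a sum is the only operation given, and SAP 9.1.3 closes off other imputation. LOCF does not help, because it replaces a missing endpoint and a form that passes the thresholds is not missing. That blanks differ between arms is possible in an open-label trial, but the documents give no evidence of it.

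**Conclusion.** The concern holds for incomplete forms. A plain sum with minimum counts of 12 of 18 and 5 of 9 understates the total by up to 33% and a domain by up to 44%. The sensitivity analysis carries a shortfall of up to 28% in the total that is purely an artefact of deletion. The percentages hold for uniform answers on any unit; the point values assume 1-7 items. How often it matters in the main score depends on the number of blanks, which the documents do not give.

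For item direction, the finding is a missing statement. It would be wrong to conclude that the score is prescribed in the wrong direction, since the 50 mm check presupposes recoding. If the sum were nevertheless programmed literally, the range would fall to 44% of its correct size, with a standardised effect of 0.83-0.99 for the total and 0.62-0.96 for vomiting under assumed item correlations of 0.3-0.9.

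SAP 9.4 treats secondary endpoints as supportive. The primary endpoint and the sample size are not touched.

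**What to change.** Amend SAP 7.9 before database lock:

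- Recode items 3, 6, 11, 15 and 18 before any scoring, and state the item unit (mm or 1-7) and the direction of the score.
- Score each domain as 9 × the mean of answered items when at least 5 of 9 are present, and the total as the sum of the two domains. Keep the existing requirement of at least 12 of 18 items; without it, two domains of 5 would allow a total from 10 items.
- Apply the 50 mm check after recoding, and use the same rescaled score in the sensitivity analysis.

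The cost is a few lines of SAP text and derivation code, with no new data.

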8.1. Analysis Sets

8.1.1. Total Set

The Total Set will consist of all patients who were enrolled into the study.

8.1.2. Full Analysis Set

The Full Analysis Set (FAS) will consist of all randomized patients to whom study drug is dispensed. It will be the primary basis for the analyses of efficacy. Following the intent-to-treat principle, patients in the FAS population will be analyzed according to the treatment to which they were randomized.

8.1.3. Per Protocol Set

A Per Protocol (PP) population will consist of all patients in the FAS population who complete the study fully compliant with the protocol and without any major deviation. Patients in the PP population will be analyzed according to the treatment they actually received. Efficacy analyses based on the PP population will be considered supportive.

8.1.4. Safety Set

The Safety population is defined as the set of all randomized patients with at least one documented application of any study drug. It will be the basis for the analyses of safety. Patients in the Safety population will be analysed according to the treatment they actually received.

8.2. Protocol Deviations

List of protocol deviations (list of subjects to be excluded from the Per Protocol set) will be created and agreed before database lock and execution of statistical analysis.

For the Per Protocol set major protocol deviations will be reasons for exclusion. Minor protocol deviations do not lead to exclusion from Per Protocol set.

Following deviations will be monitored, but other deviations might also be considered after discussion:

- Any inclusion criterion not fulfilled.
- Any exclusion criterion violated.
- Study visits not corresponding to study design

9. Statistical Methodology and Specification of Sample Size

This section describes the data analysis in details. The statistical methods are planned in accordance with the study protocol and in accordance with ICH Topic E9 Statistical Principles for Clinical Trials.

9.1. General Principles

The SOP.111 Statistical analysis of clinical data describes generally the procedure for carrying out statistical analysis of clinical data and has to be followed during inspection of data and analyses as well as instruction in this SAP.

Statistical software SAS (version 9.4 or higher)[3] will be used for analysis and for generation of tables, figures and listings (TFL).

All tables and listings will be presented by treatment groups. The tables related to a baseline will include a 'Total' column. The listings will present data from the eCRFs by patient. The listings will be created only when summaries are not sufficient for a given type of data.

9.1.1. Descriptive Statistics

Standard descriptive statistics are used in the analysis; all results are described by number of samples in the base for given computation; valid N is also reported in case of missing values in continuous variables. Median supplemented by 5th – 95th percentile range (or alternatively min-max or interquartile range) are used for continuous variables. Mean supplemented by standard deviation or 95% confidence interval is adopted for continuous variables (geometric mean and its 95% confidence interval can be presented for log-normally distributed data).

Categorical data are described using absolute and relative prevalence (frequencies) of categories; missing values can be included in the computation of categories percentages when necessary.

Results will be presented overall or if appropriate by study arms.

Figures used to illustrate selected summary tables will always refer to the number of patients included in the analysis set.

9.1.2. Rounding

The protocol does not specify any rules for rounding, therefore, following rules will be used:

- Mean (geom. mean) +1; standard deviation +2, median +1, min/max +0, confidence intervals (CIs) +1
- Percentages in frequency tables will be displayed to one decimal place
- All p-values will be rounded to three decimal places

9.1.3. Missing Data

Missing data on the primary and secondary efficacy endpoints will be imputed by multiple imputation (MI) procedure and using last observation carried forward (LOCF), as described in Section 9.4.1. Other missing data will not be imputed, except for missing times and dates, as described in Section 7.7.

9.1.4. Validation of Data

The data will be controlled in the context of other recorded data. The statistical monitoring will include evaluation of the consistence and variability of data, systematic or serious mistakes within the particular centres and between centres. Effort will be taken to identify mistakes resulting in records with non-sensical or impossible values, incorrect continuity of dates or systemic errors resulting in incorrect or missing values. This will include, among others, dates of

visits, starting/ending dates of treatment or dates of AEs, whose inaccuracy would significantly lower the reliability of results. Data from FLIE, MAT and HEOR questionnaires and Patient's Diary, are crucial for endpoint analyses and their correctness is of great importance. Data from digitalized sources (FLIE and MAT questionnaires, Patient's Diary) will also be paid close attention to, as the digitalization process is another potential source of errors. Errors will be analyzed to determine whether they occur at random or if there is any systematic failure. If a systematic failure is suspected, effort will be taken to find its source (e.g. a particular centre).

Quantitative endpoint variables used for statistical testing will be checked for their distribution using visual inspection of histograms and tested by Shapiro-Wilk test. Presence of outliers should be discussed.

9.1.5. Validation of Statistical Programming

There are three levels of validation defined (described in detail in internal IBA SOP.114 Statistical Programming):

- Level 1: Validation by a programmer (author of the program)
- Level 2: Validation by an independent programmer
- Level 3: Reprogramming by an independent programmer

Each statistical program will be validated at Level 1 at minimum. The most important analyses (primary and secondary endpoints) will be validated at level 2 or 3. If there are any figures produced in R, they must be compared visually by the analogous figures produced in SAS.

The second statistician or data analyst will check the final results. The check will include following:

- The double programming of the primary and secondary efficacy analyses and of frequency tables of adverse events
- Check of disposition of subjects in analysis sets
- Review of other outputs
- Check of errors and unexpected warnings in logs of all programs used for analysis and data preparation

In statistical programs (scripts), any corrections or updating of study data has to be documented in statistical report if the modification in clinical DB or source data was not done till the DB lock. Namely, this refers to the cases when subjects or the data are added/changed using a script rather than updating the DB. This kind of hard coding is usually proposed to correct deficiencies in the DB (missing values, wrong values, and wrong measurement units).

The hard coding may not be done in any programs used for the creation of analysis data sets, tables, listings, or analyses that are intended for external reporting after DB lock (i.e. clinical study reports/all phases/, publications, abstracts, etc.).

Since no changes are made to the study data without appropriate documentation from the investigator sites and appropriate audit trails within the clinical trial DB, this process ensures integrity of clinical data.

In very exceptional situations, when there is no other way how to correct deficiencies in the database, the hard coding may be allowed, if approved by the Sponsor. It has to be appropriately documented, at minimum in the CSR.

9.2. Determination of Sample Size

A sample of 410 randomised subjects, each scheduled to be measured 3 times/cycles, achieve a 80% power when using a two-sided Wald test from a GEE analysis to test whether the proportion of Complete response expected in the Test group (71%) differs from that expected in the Control group (60%) at a significance level of 0,050. The subjects are randomly split between a Test group and a Control group, with 50% of the subjects assigned to the Test group. The measurements of each subject will be made at the following times/cycles expressed as proportions of the total study time: {0%; 50%; 100%}. Missing values are assumed to occur completely at random (MCAR) or at random (MAR). These missing value proportions will be combined to form the pairwise observant probabilities using the Independent method. The anticipated proportions missing at each measurement time/cycle are {0%; 7.5%; 15%}. Based on these attrition rate scenario, a sample of 348 completer subjects is expected. The correlation between observations on the same subject is assumed to be 0.5 (ballpark estimate). All computations are performed using PASS 14 software.

9.3. Description of Baseline Characteristics

Demographic, physical characteristics and medical history data will be tabulated, using the standard sets of summary statistics as defined in Section 9.1.1.

All demographic and other baseline characteristics will be presented for the FAS and the data will be presented by treatment groups and overall. All details will be listed.

9.4. Analysis of Efficacy

All efficacy analyses will be performed on the FAS population. Also, analysis of the primary and secondary efficacy variables will be carried out on the Per Protocol population to assess the robustness of the findings.

The overall type I family-wise error rate for testing the primary and the secondary efficacy parameters is controlled at the 0.05 significance level without the need to adjustments since the study is planned with a single primary endpoint and since secondary endpoints are only supportive of primary endpoint findings. All statistical analyses will be performed using SAS version 9.4 or later.

Information on nausea and vomiting during the acute and delayed phase and overall from MAT will be considered for analysis. For analysis of daily occurrences, MAT information will be used for Day 1 (identical to acute phase), otherwise data from Patient's Diary will be used.

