### 3.5. Study Endpoints

Definition of the assessment of time-related study efficacy endpoints:

Time-related efficacy study endpoints assessment will start at time 0 defined as the start time of the chemotherapy administration on Day 1 of each of the three cycles.

CINV indicators, such as nausea and vomiting, their intensity and frequency and Quality of Life will be evaluated during the acute phase of emesis, from 0 to 24 hours from the start of chemotherapy, in the delayed phase of emesis, from 24 to 120 hours from the start of chemotherapy, and overall during each day (i.e., day 1, 2, 3, 4 and 5) from the start of chemotherapy.

The primary endpoint will be the proportion of complete responses (no emetic episode and no rescue medication), during the overall phase (0-120h), after the start of the MEC administration over three cycles of chemotherapy.

Clinical secondary endpoints will be evaluated during each cycle:

- Complete response during the acute (0-24h), delayed phase (>24-120h), overall (0-120h) and daily in each cycle;
- No emetic episode during the acute, delayed and overall phase and daily in each cycle;
- Number of vomiting episodes during the acute, delayed and overall phase and daily in each cycle;
- No rescue medication during the acute, delayed and overall phase and daily in each cycle;
- No significant nausea (maximum MAT scale = 2) during the acute, delayed and overall phase and daily in each cycle;
- No nausea (MAT scale = 0) during the acute, delayed and overall phase and daily in each cycle;
- Complete protection (no emetic episode, no rescue medication and no significant nausea) during the acute, delayed and overall phase and daily in each cycle
- Nausea and Vomiting-related quality of life indicators (through the Functional Living Index Emesis scale)
- Collection of chemotherapy delays and/or dose reductions (Delay of chemotherapy administration due to CINV will be also evaluated as part of health economic endpoints, see below)

Health economic endpoints will be evaluated during the study cycles:

- Number of days and daily doses of rescue medication administered for the treatment of CINV
- Number of re-hydration bags given for at least grade 2 vomitings (CTCAE v5)
- The number of days of unplanned hospitalisations related to CINV and department of hospitalization (type of ward)
- The number of outpatient physician visits and health care consultations due to CINV (e.g., general practitioner)

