4.2. Secondary Objectives

The secondary objectives are:

- To evaluate acute (0 to 24 hours), delayed (>24 to 120 hours), and overall (0 to 120 hours) CINV indicators in each cycle of chemotherapy
- To evaluate the predictive role of potential risk factors in the development of CINV over three cycles of chemotherapy
- To evaluate the safety profile of the antiemetic drug over three cycles of chemotherapy
- To explore the effect of CINV on daily activities and quality of life in patients receiving moderately-emetogenic chemotherapy over three cycles of chemotherapy
- To evaluate resource utilization and health economic outcome

Time 0 is defined as the start time of the chemotherapy administration on Day 1 of each of the three cycles. CINV indicators are nausea and vomiting, their intensity and frequency and Quality of Life in the acute, delayed and overall period.

Information on CINV indicators during acute and delayed phase will be taken from MAT questionnaires. Daily information (apart from Day 1) will be taken from Patient's Diary.

Potential risk factors for CINV thought to be increasing the risk of CINV in patients receiving MEC are reported in section 3.3.3 of the study protocol. Risk factors for CINV are described also in section 3.6.3.1 of the study protocol where risk score algorithm calculation by using predictive factors for CINV is explained.

5. Study Design

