Functional Living Index-Emesis (FLIE) questionnaire, a validated, nausea and vomiting specific, patient-reported outcome instrument. The frequency and intensity of acute and delayed nausea and vomiting will be measured via MAT. Rescue medication will be allowed at any time, during every cycle. The choice will be left at the discretion of the Investigators. The intake of rescue medications, either prescribed or non-prescribed, must be recorded in the Patient's diary and in the eCRF.

Patients may withdraw the study at any time at their own willing, without giving further details or justification.

The investigator may also exclude a subject from the study on the basis of his/her clinical judgment:

- General or specific changes in the patient's condition which make the patient ineligible for further assessments according to the inclusion/exclusion criteria
- Non-qualification to perform consecutive cycles (e.g., for toxicity)
- Failure to return for follow-up visits

The planned study enrolment time will be 12–18 months, with each patient making maximum of 5 visits in total.

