9.4.1. Imputation of endpoints data

To achieve the largest possible sample, imputation techniques will be used to impute missing data for the FAS population. Missing data on the primary efficacy endpoint will be imputed using conventional Multiple Imputations approach. The SAS® MI procedure will be employed to perform multiple imputation in order to obtain Maximum Likelihood estimates which, by definition, are unbiased under a MCAR and MAR mechanism for missing values.

The following MI procedure code will be used to perform MI with 5 imputations.

```
PROC MI data = dataset seed=s out = MIdataset n impute = 5;
VAR study_treatment carboplatin country vis1_event - vis3_event;
CLASS study_treatment carboplatin country vis1_event - vis3_event;
monotone logistic;
RUN;
```

The exact names of the variables may differ.

9.4.2. Missing data within the FAS population on secondary efficacy endpoints will be imputed using the last observation carried forward (LOCF). Primary Efficacy Endpoint

The primary efficacy endpoint “Proportion of complete responses over three cycles of chemotherapy after the start of the MEC administration” will be analyzed by means of a generalized linear model (GLIM) with logit link function, binomial distribution and with “study treatment” (NEPA + Dex or Standard of care), “carboplatin use” (yes or no) and “country” as factors, using data from the overall period of three cycles.

Moreover, the GLIM model will be parameterized with generalized estimating equations with an exchangeable working correlation matrix to take into account clustered data (i.e. three repeated measures corresponding to as many cycles of chemotherapy within each subject). Results will be reported as odds ratios with associated two-sided 95% confidence intervals and p-values.

The results will be obtained via the GENMOD procedure, using following code:

```
PROC GENMOD data = dataset;
CLASS id study_treatment carboplatin country;
MODEL complete_response = study_treatment carboplatin country / dist = bin
link = logit;
REPEATED subject = id / type = exch covb corrw;
LSMEANS study_treatment / diff exp ilink cl;
RUN;
```

The exact names of the variables may differ.

With MI the code will be modified to:

```
PROC GENMOD data = dataset;
CLASS id study_treatment carboplatin country;
MODEL complete_response = study_treatment carboplatin country / dist = bin
link = logit;
REPEATED subject = id / type = exch ecovb;
LSMEANS study_treatment / diff exp ilink cl;

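### The SAP takes delayed and overall vomiting from the MAT alone, and the MAT delayed page can be completed up to 24 hours before the 0-120 h primary window closes

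*SAP*

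**What the plan says.** The primary endpoint is complete response, meaning no emetic episode and no rescue medication, assessed "during the overall phase (0-120h), after the start of the MEC administration over three cycles of chemotherapy" (Protocol 3.5). Time 0 is the start of chemotherapy on Day 1 of each cycle.

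The SAP assigns a data source to each phase:

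- SAP 4.2: "Information on CINV indicators during acute and delayed phase will be taken from MAT questionnaires", followed by "Daily information (apart from Day 1) will be taken from Patient's Diary".
- SAP 5.1: "The frequency and intensity of acute and delayed nausea and vomiting will be measured via MAT".
- SAP 9.4: "Information on nausea and vomiting during the acute and delayed phase and overall from MAT will be considered for analysis". It adds: "For analysis of daily occurrences, MAT information will be used for Day 1 (identical to acute phase"), with the diary for the other days.
- SAP 7.9 pools the acute and delayed MAT data to form the MAT scale for the overall phase.
- Rescue use follows a different route: "The intake of rescue medications, either prescribed or non-prescribed, must be recorded in the Patient's diary and in the eCRF" (SAP 5.1). The MAT in Protocol Appendix 3 has no rescue question.

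On timing, the MAT delayed page (Appendix 3) asks about the period that starts the day after chemotherapy and runs to four days after it. The form and Protocol 7 have it completed four days after chemotherapy. The visit instructions in Protocol 3.6.3.2 to 3.6.3.4 say Day 5. The diary records the number of emetic episodes from Day 1 to Day 5 (Protocol 3.6.2).

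**The concern.** The source chosen for the vomiting half of the primary endpoint need not reach the end of the window, while the source left out does record that time. The rescue half comes from the diary and eCRF, so the two halves of one endpoint can cover different spans. Late rescue use is captured. Late vomiting without rescue can be lost even though the patient wrote it down.

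The same cycle can then be a responder for the overall phase and a failure for Day 5. Planned Table 14.2-2 reports the overall-phase and daily results together. A primary result that may not cover its stated window, and tables that can disagree with no rule for deciding between them, are the main stakes.

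The rule is best settled now. The trial is open label, and SAP 9.9 allows endpoint frequencies by arm to be summarised for single countries before the final analysis.

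**Working it through.** **1. Window against form.** SAP 9.4 equates Day 1 with the acute phase, 0-24 h. Day k therefore runs from 24(k-1) to 24k hours, and Day 5 is 96-120 h.

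- Primary window: 0-120 h.
- Earliest completion of the delayed page under the instructions: four days × 24 = hour 96, the start of Day 5.
- Largest uncovered stretch: 120 - 96 = 24 h, which is 24/120 = 20% of the overall window and 24/96 = 25% of the delayed window.
- Smallest: close to zero, if the page is completed at the end of Day 5.

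The FLIE is set for Day 6, after the five days have closed. The MAT has no such margin.

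**2. One cycle followed through.** Suppose the MAT delayed page is answered no at hour 96, the patient vomits once at hour 110 without rescue, and the Day 5 diary records it.

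- Overall phase (MAT for vomiting; diary and eCRF for rescue): complete response.
- Day 5 (diary): failure.

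**3. Does another rule settle it?**

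- Protocol 3.6.3 has the investigator complete missing answers with the patient. A no given at hour 96 is not missing.
- SAP 3 and 9.1.4 and Protocol 7 call for discrepancy checks, consistency checks and queries. None says whether MAT or diary decides.
- SAP 9.9 requires complete information on both MAT and diary, but only for the descriptive country summary.

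**4. Reproducing the planned power.** Inputs from SAP 9.2: 410 patients, so 205 per arm; 60% v 71%; correlation 0.5; proportions observed φ = 1, 0.925, 0.85, combined as independent pairs; two-sided 0.05.

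- Σφ = 2.775, and the sum of φᵢφⱼ over i≠j is 5.1225.
- Information per patient = 2.775² / (2.775 + 0.5 × 5.1225) = 1.443.
- Var(log OR) = [1/(0.60×0.40) + 1/(0.71×0.29)] / (205 × 1.443), giving SE = 0.1746.
- log OR = 0.4899 (OR 1.632); z = 2.805; power = Φ(2.805 - 1.960) = 80.1%.

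The stated 80% reproduces. Exchangeable weighting gives 80.6%.

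**5. Illustration of missed late vomiting.** All miss rates are assumed, because the documents give none. The formula is that of step 4.

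| Failures missed | Observed rates | OR | Power |
|---|---|---|---|
| None | 60 v 71 | 1.632 | 80.1% |
| 1 point in each arm | 61 v 72 | 1.644 | 80.6% |
| 2 points in each arm | 62 v 73 | 1.657 | 81.2% |
| 5% of failures in each arm | 62.0 v 72.45 | 1.612 | 77.0% |
| 10% of failures in each arm | 64.0 v 73.9 | 1.593 | 73.7% |
| 2 points control, 1 point test | 62 v 72 | 1.576 | 73.2% |
| 1 point control, 2 points test | 61 v 73 | 1.729 | 87.1% |

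One point is about 5.7 of the 205 × 2.775 = 568.9 expected cycles per arm. The 87.1% reflects an inflated effect and is not a gain in power.

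**The case against.** The strongest reply is that the affected case is narrow. The cycle's only vomiting must come after the MAT page is completed, before hour 120, and without rescue, since rescue already reaches the endpoint by another route. Many patients may complete the page late on Day 5 and cover nearly the whole window. Investigators collect and review both forms, and the investigator signs the diary as checked, so a MAT no against a Day 5 diary yes could be queried before lock. All of that stands, and it limits the likely size. It does not supply the missing rule, because a query about two honestly completed forms still needs a stated source to decide the endpoint.

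Three stronger readings are tempting, and the documents do not support them.

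- A reader might infer that late-completed pages count vomiting after 120 h, because item 5 of the MAT states no upper limit. The header of that page does bound the period, at four days after chemotherapy.
- A reader might count Day 5 as a calendar day and find a gap longer than 24 h. SAP 9.4 makes Day 1 identical to the acute phase, which caps the gap at 24 h.
- A reader might infer that a blank Day 5 diary should make the cycle missing and that the "monotone logistic" statement in SAP 9.4.1 must then be replaced. The missing rule would itself create the non-monotone gaps. The source rule below needs neither change.

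**Conclusion.** The point holds as a gap in endpoint ascertainment and pre-specification. Followed as written, the SAP can leave up to 24 h of the 120 h primary window without vomiting data while the diary holds those data, and no text says which source prevails. The 24 h figure rests on Day 5 being 96-120 h, as SAP 9.4 implies, and on completion at the earliest instructed time.

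A reader might go further and infer a biased treatment effect or an underpowered trial. The documents do not support that. They give no rate of late unrescued vomiting and no reason for misses to differ between arms. With small, similar misses (up to 2 points, or 5% of failures, in each arm) power stays at about 77% to 81%. The larger movements in the table need a bigger or unequal miss rate, and each of those is an assumption. No stated figure in the sample size section is wrong on this account.

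**What to change.** In SAP 4.2 and 9.4:

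- **Delayed phase:** define no emetic episode as no vomiting on the MAT delayed page and none on diary Days 2-5.
- **Overall phase:** the same, plus no vomiting on the MAT acute page.
- **Conflict:** a positive report in either source within 0-120 h makes the cycle a failure.
- **Scope:** apply the same source rule to complete response, complete protection and number of vomiting episodes. For the count, say how MAT and diary totals are combined, so that an emetic failure cannot appear with zero episodes.
- **Mapping:** state that diary Day 5 is 96-120 h, in line with SAP 9.4.
- **Sensitivity:** repeat the primary analysis once with vomiting taken from the MAT only.

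The cost is SAP wording and one extra run on data already collected. A few cycles move from response to failure. A small gap can remain: the diary pages that could be read (Days 3 and 4) carry no clock time, and a Day 5 page may itself be filled in before hour 120.

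A separate matter for the protocol: Visit 4 may fall on Day 5 of cycle 3 (3.4.4, 3.6.3), when the Day 5 diary may be incomplete and the FLIE is not due until Day 6 (3.6.3.4). Those passages must be reconciled.
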